A prospective randomized clinical trial evaluating the effect of convective pre-warming on intra-operative thermoregulatory capabilities in patients enrolled in the TIGER anesthesia perioperative protocol

PI: [name], BS¹
Medical Student

Co-PI: [name], MD²
Professor

Co-I: [name], CRNA²

Co-I: [name], RN²

Co-I: [name], MPH²

¹University of Missouri School of Medicine

²Department of Anesthesiology and Perioperative Medicine

University of Missouri
[name]

NCT03876808

Contact: [name], BS

University of Missouri School of Medicine

[name]

[name]

[contact]

Email: [contact]

Summary

This prospective randomized clinical trial will assess the effect of pre-operative convective warming on intra-operative thermoregulation in patients undergoing gastrointestinal or genitourinary surgical procedures with the TIGER* anesthesia perioperative protocol.

*See addendum 1

Objectives:

Primary Endpoint:

1. Change in core temperature between induction of anesthesia and end of skin preparation (but before turning on the operating room forced-air warmer) as measured by a temperature-sensing Foley catheter

Secondary Endpoints:

1. Change in skin temperature between arrival to the holding area and departure to the operating room
2. Intraoperative temperatures
3. Skin temperature on arrival to the PACU (post-anesthesia care unit)
4. Differences in temperature changes between elderly (≥ 65 years) and younger patients

Clinical Hypotheses:

Primary Hypothesis:

We hypothesize that patients who are convectively warmed at 43°C for at least 60 minutes pre-operatively will have a higher core body temperature during the intraoperative period as measured by a temperature-sensing Foley catheter

Exploratory Hypothesis:

Patients who are convectively warmed prior to surgery will have

1. Temperatures that are significantly increased
 - a. At departure from the preoperative holding area

- b. In the OR after surgical preparation
 - c. On arrival to the PACU
2. Older (age \geq 65 years) patients will demonstrate a greater change in mean intraoperative temperature compared to younger patients

Background & Rationale:

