was a significant difference in severity of hypothermia when it did occur.¹³ This study focused only on men undergoing transurethral resection of the prostate however, and suffers from lack of generalizability. With the proportion of the geriatric population continuing to expand, and the potential adverse effects resulting from their increased susceptibility to intraoperative hypothermia, it is of the utmost importance to look into methods to counter this dilemma and expand the database on the topic.

Study Design:

This will be a prospective randomized clinical trial performed at a single academic hospital. Due to the nature of the trial, the anesthesiologists and subjects will not be blinded to their group assignment, but the postoperative assessments will be. All subjects will receive standardized pre-operative preparations, induction, and intraoperative infusions, as dictated by the TIGER anesthesia perioperative protocol.

In addition to these measures, one group will undergo convective warming during the preoperative preparations, completed for a minimum of 60 minutes prior to entering the operating room, while the other group will undergo standard of care, which includes providing each patient with a warming gown that is not turned on as well as blankets and sheets with more blankets provided on patient request.

Study Procedures:

- I. Patient population: 40 patients undergoing gastrointestinal or genitourinary surgeries, who are enrolled in the TIGER anesthesia perioperative protocol
- II. Inclusion criteria:
 - a. ASA I-IV
 - b. Other inclusion criteria as delineated in the TIGER anesthesia perioperative protocol
- III. Exclusion criteria:
 - a. Inability to obtain written informed consent
 - b. Inability to obtain Foley catheter temperature recordings
 - c. Family history of malignant hyperthermia
 - d. Preoperative temperature $> 38^{\circ} \text{ C}$
 - e. Other exclusion criteria as delineated in the TIGER anesthesia perioperative protocol
- IV. Randomization: On the day of surgery, patients will be randomized to one of two groups:
 1. Warming group: This group will undergo pre-warming at a temperature of 43° C or a minimum of 60 minutes beginning upon arrival to the pre-operative room continuing until they are taken to the operating room. This will be achieved with blankets as well as the use of a Bair Hugger® heating gown.

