 2. Standard of care group: this group will receive the standard of care during the preoperative period, which includes providing the patient with blankets and sheets, as well as additional blankets upon request. They will also wear a Bair Hugger® heating gown, but it will not be used for preheating prior to surgery.

V. Randomization will be stratified for the type of surgery (gastrointestinal versus genitourinary) in an effort to reduce confounding.

VI. Blinding: Due to the nature of this study, the anesthesiologist, nursing staff, operating room staff, and the subject will know to which group the subject has been assigned.

VII. Anesthetic management as outlined in the enhanced recovery protocol.

VIII. Postoperative pain management as outlined in the enhanced recovery protocol.

IX. Perioperative assessments

- a. Duration of pre-warming prior to surgery
- b. Temperature change from arrival in the pre-operative holding area to leaving for the operating room as measured by a skin-temperature thermometer.
- c. Temperature change, as measured by a Foley catheter sensor inserted, after induction of anesthesia to the end of surgical skin preparation.
- d. Temperature as measured with a Foley catheter sensor throughout the operative procedure.
- e. Temperature change between leaving the operating room and arrival in the Post Anesthesia Care Unit (PACU).
- f. Duration of hospital stay, estimated blood loss, transfusion requirements, and postoperative complications

X. Sample size and statistical consideration:

- a. This is a pilot study and, if pre-warming is successful at preventing intraoperative hypothermia, data from this study will be used to develop larger studies. We plan to enroll 20 patients per group for a total sample size of 40 subjects to obtain pilot data.
- b. Data will be analyzed using chi-square and t-tests as appropriate with $p < 0.05$ considered significant.

Risks:

- I. No adverse effects are currently expected through participation in this study other than possible sweating and discomfort in patients in the pre-warming group heated for more than one hour.
 - a. Patients in the pre-warming group will be warned of the potential for sweating or discomfort due to warmth during informed consent at the pre-operative clinic visit. If they feel uncomfortable during the pre-warming process, staff will turn down the warmers from 43C to 38C; if symptoms persist staff will turn the warmers off.

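### The elderly-versus-younger comparison is not randomised, and the plan names no adjustment for surgery type; stratified randomisation does not supply one

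*Combined protocol and SAP*

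**What the plan says.** The age comparison appears twice. Under Objectives, secondary endpoint 4 is "Differences in temperature changes between elderly (≥ 65 years) and younger patients". Under Clinical Hypotheses, exploratory hypothesis 2 states that older "patients will demonstrate a greater change in mean intraoperative temperature compared to younger patients". That hypothesis is listed beneath a stem about patients who receive convective warming, and the plan does not say whether it concerns all patients, warmed patients only, or a difference in the effect of warming.

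What is randomised is warming against standard of care (Study Procedures, IV): "On the day of surgery, patients will be randomized to one of two groups". Item V adds: "Randomization will be stratified for the type of surgery (gastrointestinal versus genitourinary) in an effort to reduce confounding". Age is not a stratification factor.

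The analysis text is one sentence, Study Procedures X.b: "Data will be analyzed using chi-square and t-tests as appropriate", with a 0.05 significance level. It names no covariate, regression model, stratified analysis or interaction, and does not mention age. On size, X.a says: "We plan to enroll 20 patients per group for a total sample size of 40 subjects to obtain pilot data". The study is described as a pilot.

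**The concern.** Randomisation, with or without strata, protects only the comparison of the groups it creates. Patients arrive with their age and their type of surgery, and nothing in the eligibility criteria or the randomisation constrains how the two go together. If older patients have relatively more genitourinary (or more gastrointestinal) operations, any difference in temperature change between the two kinds of surgery is carried into the comparison of older with younger patients.

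The result could be an apparent age effect that is partly a surgery-type effect, or a real age difference that is masked. A larger sample would not remove this; it would only estimate the mixed quantity more precisely. The question matters to the authors: the Background is built around the elderly and the scarcity of evidence on pre-warming them, and X.a says the pilot data will feed larger studies.

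**Working it through.** **Plan's own figure.** The documents give no calculation for the age comparison. The only sample-size figure is 20 + 20 = 40, with no power, SD or effect size.

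**Inputs.** From the documents: 40 patients, two surgery types, a 0.05 level (taken as two-sided) and a t-test. Assumed, because the documents are silent: the number of patients aged 65 or over (14 of 40 as the main case), the share of genitourinary surgery in each age group, and the effect g of surgery type on temperature change, in units of the residual SD (0.5 to 1.0).

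**Bias.** With no true age effect, the expected unadjusted difference is

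bias = g × (genitourinary share in older − genitourinary share in younger).

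- Shares 60% v 40%: 0.5 × 0.20 = 0.10 SD, and 1.0 × 0.20 = 0.20 SD.
- Shares 70% v 35%: 0.5 × 0.35 = 0.175 SD, and 1.0 × 0.35 = 0.35 SD.
- Equal shares: g × 0 = 0.

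Which surgery type is the more common in older patients changes only the sign.

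**False-positive rate of the unadjusted t-test.** Simulated with no true age effect, surgery type drawn at random for each patient, and 20,000 to 40,000 trials per setting:

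| Patients (older v younger) | Shares | Bias (SD) | False-positive rate |
|---|---|---|---|
| 14 v 26 | equal | 0 | about 5% |
| 14 v 26 | 60% v 40% | 0.10 to 0.20 | about 6% to 8% |
| 14 v 26 | 70% v 35% | 0.18 to 0.35 | about 8% to 15% |
| 7 v 13 (warmed only) | 60% v 40% | 0.10 to 0.20 | about 5% to 7% |
| 7 v 13 (warmed only) | 70% v 35% | 0.18 to 0.35 | about 6% to 10% |

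**Sensitivity to the age split and the mix.** With 20 v 20 patients and the surgery counts held fixed, a 40/60 mix gives 5.3% to 6.2%, a 30/70 mix 9.0% to 17.4%, and a 20/80 mix 14.6% to 39.5%. The last is an extreme case, shown only to mark the range.

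**After adjustment.** With surgery type added to a linear model alongside age group, the estimated age difference returns to about 0 in all these settings and the false-positive rate to about 5%.

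**Why arm also belongs in a pooled analysis.** Age is not stratified, so warming can be unevenly spread over the age groups by chance. Ignoring the surgery strata, the hypergeometric probability that the warmed share differs by 20 percentage points or more is about 34% with 20 v 20 patients and about 27% with 10 v 30.

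**If the question is whether warming works differently by age.** Warming is randomised within each age group, so a main effect of surgery type cancels in expectation from the age-by-arm contrast. Only a warming effect that itself differs by surgery type could distort it. A model with age, surgery type and arm but no age-by-arm term would not answer this question.

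**The case against.** Several points on the other side stand.

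- A reader might infer that the plan prescribes an unadjusted t-test for age. It does not: X.b never mentions age and adds the qualifier that tests are used as appropriate. What can be said is that no method is specified for this comparison, and that the t-test is the only one named for a continuous outcome.
- A reader might infer that the protocol acknowledges surgery type as a confounder of the age comparison. Item V gives a reason for stratifying the randomised arms. It says nothing about surgery type being related to age.
- Both drivers are assumed. A surgery effect of 0.5 to 1.0 SD is moderate to large. Two of the planned temperature changes (holding area to departure, and induction to end of skin preparation) end before the operation starts, under preparation and induction that the Study Design describes as standardised. Nothing in the documents supports an effect of that size for those windows. At 60% v 40% the inflation is only about 1 to 3 percentage points.
- Bias presumes an interest in age as such. As a plain description of how older and younger patients differed, the unadjusted difference is valid.
- This is one secondary and exploratory comparison in a 40-patient pilot.

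None of this restores the protection that stratification might seem to give. It limits the size and certainty of the problem, not its logic.

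**Conclusion.** The point holds as a minor, conditional weakness. As written, the plan offers only an unadjusted method for a non-randomised comparison, and its stratification does not help there. The distortion needs both a different surgery mix by age and an effect of surgery type on temperature change. If either is absent it vanishes. It is small at a 60% v 40% mix and becomes material at about 70% v 35%. It is smaller if only warmed patients are compared, and largely absent if the question is a different warming effect by age.

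The documents do not support the stronger conclusion that the age result will be wrong, since they give no mix and no surgery effect. Nor would adjusting for surgery type isolate an effect of age: other characteristics that may vary with age, such as ASA class (I to IV are eligible), would remain. The randomised primary comparison is untouched.

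**What to change.** First, state whether secondary endpoint 4 and exploratory hypothesis 2 concern all patients, warmed patients only, or a different effect of warming by age.

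Then replace the implied t-test for this question with a linear model containing age group and surgery type. Add randomised arm if both arms are pooled, and an age-by-arm term if a different warming effect is intended. Report the adjusted age difference (or the age-by-arm estimate) with a 95% CI, and describe it as an exploratory association, because other age-related differences remain unadjusted.

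The cost is one sentence of analysis text and one to three degrees of freedom: one for surgery type, one for arm if used, and one for the age-by-arm term if used. No new data are needed, since surgery type and arm are already known from the stratified randomisation.

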By the year 2030 the geriatric presence in the United States, defined as any adult >65 years of age, is estimated to reach around 20% of the entire population.¹ Thus, understanding medical concepts as they relate to the elderly is becoming increasingly important. One such concept is that of hypothermia - a core body temperature $< 36^{\circ}\text{C}$ - for which age >65 has been found to be an independent risk factor.² This complication is especially prevalent intra-operatively due to use of general anesthetics, cool ambient operating room (OR) temperatures, and impaired thermal regulation in the elderly.³

The human body employs numerous mechanisms to maintain thermal homeostasis including: behavioral means of thermoregulation, sweating, pre-capillary vasodilation, non-shivering and shivering means of heat production, and arteriovenous shunt vasoconstriction.⁴ The first, and arguably most important, regulatory response to occur is that of vasoconstriction, which normally results in redistribution of blood from the relatively cool periphery to the warmer core compartment in order to confine metabolic heat to the central tissues.^{2,5} Patients undergoing general anesthesia experience reduced vasoconstriction due to decreased cold response thresholds while patients undergoing epidural anesthesia experience sympathetic blocks resulting in blunted vasoconstrictive responses.^{2,5} All patients experience the afore mentioned side effects of anesthetics, however it has been proven that the elderly are more susceptible to hypothermia due to lower vasoconstriction thresholds - determined by a temperature gradient of 4°C between the periphery and core.

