First explored by *Kurz et al.*⁶ in 1993, it was found that use of nitrous oxide and isoflurane anesthesia lead to an approximately 1.2°C lower vasoconstriction threshold of 33.9 ± 0.6 in the elderly versus 35.1 ± 0.3 in the young ($p < .01$). This subject was again looked at in a 1997 study wherein the vasoconstriction threshold during nitrous oxide and sevoflurane was observed to be decreased by approximately 0.8°C in the elderly at 35.0 ± 0.8 versus 35.8 ± 0.3 in the young ($p < .01$).⁷ This is relevant because intraoperative hypothermia has long been known to lead to adverse outcomes such as increased incidence of myocardial ischemia, arrhythmias, coagulopathic states, and wound infections.⁴ In a 2014 retrospective cohort study by *Billeter et al.*² patients experiencing core temperatures $<35^\circ\text{C}$ had a four times increase in mortality with complication rates increasing two fold and incidence of stroke increasing six fold. To counter this thermoregulatory failure in patients, numerous methods of warming have been practiced over time to augment the normal body response.

One method used to decrease intraoperative hypothermia is warming patients before surgery via skin surface warmers. Numerous studies have found that even brief periods of pre-warming can improve intraoperative temperatures significantly for as long as 75-90 minutes after induction.^{8,9} In procedures lasting less than 90 minutes, *Horn et al.*¹⁰ found that as little as 10 minutes of pre-warming decreased incidence of intraoperative hypothermia from 69% to just 13% while *Torossian et al.*¹¹ decreased the incidence from 60% to 38% in his study using a self-warming blanket for 30 minutes pre-operatively. Studies have also shown that longer pre-warming of 45-60 minutes can prevent hypothermia for up to 2 hours after induction.¹²

[figure not shown]
While significant research has been performed on the effects of warming patients before they undergo surgical procedures, scant evidence demonstrates the effect of pre-warming in the elderly. In one article specifically looking at pre-warming in the elderly (mean age ~72-73) it was found that, after pre-warming for 20 minutes, there was no significant change in incidence of hypothermia but there

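### The primary comparison neither balances nor adjusts for age, although age is a documented risk factor and defines a secondary endpoint; adjusting for it would cost almost nothing

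*Combined protocol and SAP*

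**What the plan says.** Study Procedures, item V: "Randomization will be stratified for the type of surgery (gastrointestinal versus genitourinary) in an effort to reduce confounding". No block size or allocation method is given, and no other balancing factor is named.

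Item X.a sets the size: "We plan to enroll 20 patients per group for a total sample size of 40 subjects to obtain pilot data". It also gives the purpose: "This is a pilot study and, if pre-warming is successful at preventing intraoperative hypothermia, data from this study will be used to develop larger studies". Item X.b is the whole analysis plan: "Data will be analyzed using chi-square and t-tests as appropriate with $p < 0.05$ considered significant". It contains no covariate and no stratum term.

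The primary endpoint is: "Change in core temperature between induction of anesthesia and end of skin preparation".

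Age appears in two places. Secondary endpoint 4 is "Differences in temperature changes between elderly (≥ 65 years) and younger patients", and exploratory hypothesis 2 repeats the theme. Background & Rationale describes hypothermia as a condition "for which age >65 has been found to be an independent risk factor". It then cites two studies of vasoconstriction thresholds under anaesthesia. The 1993 study reports "33.9 ± 0.6 in the elderly versus 35.1 ± 0.3 in the young", about 1.2°C lower in the elderly. The 1997 study reports a threshold about 0.8°C lower.

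**The concern.** Item V gives a reason for stratifying, namely to limit confounding. By that reason age has a better documented claim than surgery type, for which the documents report no temperature effect. Age is known before randomisation on the day of surgery and must be recorded for endpoint 4, yet it enters neither the allocation nor the analysis.

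With 20 patients per arm, the elderly can easily split unevenly. If age affects the fall in core temperature after induction, an unadjusted comparison then carries avoidable noise. The estimate from this one trial could also be noticeably off, and it is meant to inform the design of larger studies.

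**Working it through.** **Inputs from the documents.** 40 patients, 20 per arm (X.a); surgery type as sole stratum (V); chi-square and t-tests (X.b). No effect size, standard deviation or power is stated, so there is no sample-size figure to reproduce.

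**Assumptions.** 8 to 20 of the 40 patients (20% to 50%) are 65 or over; the documents give no age mix for this trial. Age is unrelated to surgery type. Block size, where used, is 4.

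**Step 1: chance imbalance under 20/20 allocation.** With K elderly among 40, the number X in one arm is hypergeometric: P(X = x) = C(K, x)·C(40−K, 20−x)/C(40, 20). The arms differ by |2X − K|.

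For K = 8, a difference of 4 or more means X ≤ 2 or X ≥ 6. The terms for X = 0, 1, 2 are 225,792,840 + 2,778,988,800 + 13,200,196,800 = 16,204,978,440. Divided by C(40, 20) = 137,846,528,820 this is 0.1176, and doubled it is 0.235.

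| Elderly of 40 | P(difference ≥ 4) | P(difference ≥ 6) |
|---|---|---|
| 8 | 23.5% | 4.4% |
| 12 | 30.1% | 8.2% |
| 16 | 33.3% | 10.5% |
| 20 | 34.3% | 11.3% |

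A difference of 4 is 4/20 = 20 percentage points.

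**Step 2: does stratifying by surgery type help?** With two surgery strata of 20, each split 10:10 and with the elderly spread evenly, P(difference ≥ 4) is 24.2%, 30.7%, 34.0% and 34.9%. It does not help.

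A simulation with blocks of 4 within surgery type (20,000 replicates, surgery types 50:50) gave 16%, 23%, 26% and 28% at 20%, 30%, 40% and 50% elderly. In that simulation the number of elderly also varied at random. When it is odd, a difference of exactly 4 cannot occur, which explains at least part of the lower figures.

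**Step 3: what an imbalance does to the estimate.** The shift in the arm difference is (imbalance in proportion elderly) × (age effect). The age effect on the primary endpoint is not given, so take 1 residual SD as an illustration. A 20-point imbalance then shifts the estimate by 0.20 × 1 = 0.20 SD. The standard error with 20 per arm is √(2/20) = 0.316 SD, so the shift is 0.20/0.316 = 0.63 standard errors.

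If the whole 0.8 to 1.2°C threshold gap carried over to the endpoint, which the documents do not say, the shift would be 0.20 × 0.8 = 0.16°C to 0.20 × 1.2 = 0.24°C.

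**Step 4: what adjustment gains.** For an elderly share p and an age effect of 1 SD, ignoring age multiplies the SD by √(1 + p(1−p)). Estimating one extra coefficient multiplies the standard error by about √(38/37) = 1.013. The ratio of adjusted to unadjusted standard error is therefore 1.013/√(1 + p(1−p)):

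- p = 0.2: 1.013/√1.16 = 0.94
- p = 0.3: 1.013/√1.21 = 0.92
- p = 0.4: 1.013/√1.24 = 0.91
- p = 0.5: 1.013/√1.25 = 0.91

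The gain is about 6% at a 20% share and about 8% to 9% at 30% to 50%. If age has no effect, the loss is about 1.3%. Simulation agrees.

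**Step 5: what balancing on age gains.** With blocks of 4 within surgery type by age group, P(elderly difference ≥ 4) falls to 0.3% to 0.4%. The chance that total arm sizes differ by 4 or more rises from about 1.4% to about 8%, because four strata leave more incomplete blocks.

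**The case against.** The strongest reply is that this is a self-declared pilot of 40, that age is only a secondary and exploratory objective, and that the choice of a single stratification factor is a design preference that nothing in the documents contradicts. That stands as regards the stratification itself, which is why the main fix lies in the analysis.

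Four stronger readings are tempting, and the documents do not support them:

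- A reader might infer that age is the known driver of the outcome. The 0.8 and 1.2°C figures are vasoconstriction thresholds, not core temperature change from induction to end of skin preparation. They make age a plausible prognostic factor for that endpoint and no more.
- A reader might infer that age is the only prognostic factor documented. The same background also names general anaesthetics and cool operating rooms.
- A reader might infer that an uneven split confounds or invalidates the comparison. Chance imbalance after randomisation does neither; its uncertainty is already in the standard error.
- A reader might infer that balancing age would fill the evidence gap in the elderly. It adds no elderly patients. With 8 elderly split 6/2 rather than 4/4, the standard error of the arm difference among them rises by √[(1/6 + 1/2)/(1/4 + 1/4)] = √(0.667/0.500) = 1.15, or 15%. With 20 split 12/8 rather than 10/10, the rise is √(0.2083/0.2000) = 1.02, or 2%. The limit is their number. Endpoint 4 as worded also compares age groups, not arms within the elderly.

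The imbalance figures do depend on an assumed elderly share. Eligibility is partly set by the TIGER protocol, so the age mix cannot be read from these documents.

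What the reply does not meet is that an unadjusted t-test is the weaker choice when a likely prognostic variable will be recorded anyway.

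**Conclusion.** The point holds as an inexpensive improvement in efficiency and robustness; it is not a validity flaw. For an assumed 8 to 20 elderly patients, the chance of a 20-point or larger imbalance is 24% to 34% under 20/20 allocation, or about 16% to 28% in the simulation with assumed blocks of 4. Nothing in the plan corrects for it.

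The consequence is conditional. If age has an effect of about 1 SD on the primary endpoint, adjustment shortens the standard error by about 6% to 9%, and it removes a possible shift of about 0.6 standard errors when the imbalance is 20 points. If age has no effect, adjustment loses about 1%. The age effect, the elderly share and the block size are all assumptions.

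**What to change.** In X.b, replace the t-test for the primary endpoint with a prespecified linear regression of core temperature change on arm, age and surgery type, reporting the adjusted arm difference with its 95% confidence interval. State in advance whether age enters as continuous or as under 65 versus 65 and over. Surgery type belongs in the model because it is the stratification factor. The cost is one sentence and two degrees of freedom (36 residual instead of 38). No extra data, patients or visits are needed, and the change can be made even if the allocation list is fixed, provided it is made before the outcome data are examined.

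Optionally, if the list is not yet fixed, also balance on age group in item V by minimisation or small blocks. This accepts the higher chance of unequal arm totals (about 8% against 1.4% for a difference of 4 or more, with blocks of 4). It should not be done without the regression: balancing on a prognostic factor and then ignoring it makes the t-test conservative.

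The protocol should also say that neither step increases the number of elderly patients, so conclusions about pre-warming in that group will remain limited.

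### Secondary endpoint 1 is set up as a t-test on the skin-temperature change; adjusting for arrival skin temperature would usually be more precise, at almost no cost

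*Combined protocol and SAP*

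**What the plan says.** Under Objectives, secondary endpoint 1 is "Change in skin temperature between arrival to the holding area and departure to the operating room". Study Procedures IX.b lists the same quantity as a perioperative assessment: "Temperature change from arrival in the pre-operative holding area to leaving for the operating room as measured by a skin-temperature thermometer". Exploratory hypothesis 1a concerns temperatures that are significantly increased, at the time point "At departure from the preoperative holding area".

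The whole analysis plan is X.b: "Data will be analyzed using chi-square and t-tests as appropriate", with significance at p below 0.05. X.b does not assign tests to endpoints. For a continuous change compared between two arms, the t-test is the one that applies. No covariate or regression model appears anywhere. On size, X.a says: "We plan to enroll 20 patients per group for a total sample size of 40 subjects to obtain pilot data". It states no effect size, SD or power.

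Two timing statements matter. Study Procedures IV starts warming on arrival in the pre-operative room, and Ethical Considerations II.b places the Foley catheter after induction. No Foley core reading therefore precedes warming, and the arrival skin reading is the only pre-warming temperature listed in section IX.

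**The concern.** A change score subtracts the full arrival value whatever its relation to the later value. Unless the regression slope of departure on arrival temperature is close to 1, that subtraction adds noise, and chance imbalance in arrival temperature between two arms of 20 is carried into the result. A linear model estimates the slope instead of fixing it at 1.

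There is also an unsettled choice of outcome. Endpoint 1 is a change, while hypothesis 1a can be read as a departure level. Two unadjusted t-tests, one on each, can give different answers, and X.b does not say which governs. X.a intends the data for planning larger studies, so an imprecise estimate, or two that conflict, would be a poor input.

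**Working it through.** **Inputs from the documents.** 20 per arm, 40 in total (X.a); significance level 0.05 (X.b), taken as two-sided because sidedness is not stated; t-test on the change (X.b with IX.b). There is no power or precision figure in the plan to reproduce.

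**Assumptions.** rho is the correlation between arrival and departure skin temperature within arm; k is the departure SD divided by the arrival SD. Neither is given. I use rho = 0.2, 0.4 and 0.6, and k = 1, 1.5 and 2.

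**Formulas, with arrival SD set to 1.**
- Per-patient variance of the change: k² + 1 − 2·rho·k
- Per-patient variance after adjustment: k²(1 − rho²)
- Cost of estimating one slope with 40 patients: 1 + 1/(40 − 4) = 37/36 = 1.028
- Ratio, adjusted to change: (37/36) × k²(1 − rho²) / (k² + 1 − 2·rho·k)

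**Results.**

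| k | rho | change variance | adjusted variance | ratio with 37/36 |
|---|---|---|---|---|
| 1 | 0.2 | 1.60 | 0.96 | 0.62 |
| 1 | 0.4 | 1.20 | 0.84 | 0.72 |
| 1 | 0.6 | 0.80 | 0.64 | 0.82 |
| 1.5 | 0.2 | 2.65 | 2.16 | 0.84 |
| 1.5 | 0.4 | 2.05 | 1.89 | 0.95 |
| 1.5 | 0.6 | 1.45 | 1.44 | 1.02 |
| 2 | 0.2 | 4.20 | 3.84 | 0.94 |
| 2 | 0.4 | 3.40 | 3.36 | 1.02 |
| 2 | 0.6 | 2.60 | 2.56 | 1.01 |

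**Upper limit of the loss.** Change variance minus adjusted variance is (k² + 1 − 2·rho·k) − k²(1 − rho²) = (1 − k·rho)², which is never negative. So the ratio cannot exceed 37/36, a loss of 2.8%, reached when k·rho = 1. With equal SDs the ratio reaches 1 only at rho = 72/37 − 1 = 0.95.

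**Power, for illustration.** Assume equal SDs and a true difference of 0.7 SD, which is not a figure from the documents. The noncentral t gives 40%, 50% and 67% for the t-test on change at rho = 0.2, 0.4 and 0.6, against 58%, 64% and 76% adjusted. At rho = 0.8 the two are 93% and 94%.

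**Level against change.** Under the same assumptions, in 20,000 simulated trials per value of rho, the t-test on the level and the t-test on the change fell on opposite sides of p = 0.05 in about a third of trials at rho 0.2 to 0.6, and in 40% at rho 0.8. With arrival temperature X in the model, departure = a + b·arm + c·X is the same model as (departure − X) = a + b·arm + (c − 1)·X. The treatment effect b and its p-value are identical, whatever rho and k are.

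**PACU skin temperature as a level.** With equal SDs or not, the ratio of adjusted to raw variance is (37/36)(1 − rho²), where rho is now the arrival-to-PACU correlation. It falls below 1 only when rho² exceeds 1/37, that is, rho above 0.16. At rho 0 it is 1.03, at 0.2 it is 0.99, and at 0.5 it is 0.77.

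**The case against.** The strongest reply is that this is a preference about efficiency. The arms are randomized, so the unadjusted test is valid; no figure in the plan is wrong; and the endpoint is secondary in a 40-patient pilot that claims no power. All of that stands and limits the weight of the point.

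The size of the gain can also be challenged. The large gains need similar SDs at arrival and departure, but one arm is actively warmed between the readings, with a provision to lower or switch off the warmer, so equal spread cannot be presumed. At k = 1.5 or 2 the gain shrinks and can vanish. With equal SDs and high correlation it is small too (ratio 0.93 at rho 0.8, 0.98 at 0.9). This also stands, and it is why the result is a range. It does not reverse the recommendation, because the loss is bounded at about 3%.

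Hypothesis 1a speaks of increased temperatures, which can mean a rise from arrival. On that reading it matches endpoint 1 and there is no conflict, so the mismatch is conditional.

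A reader might infer three further things that the documents do not support:
- **That arrival skin temperature is the only baseline collected.** Exclusion criterion III.d requires a preoperative temperature, with no site, device or time given. It may be a separate reading.
- **That the PACU comparison certainly loses precision.** Anesthesia, surgery and operating-room warming lie between the two readings, and no correlation is given. Secondary endpoint 3 is a skin temperature level on PACU arrival, while IX.e lists a change from leaving the operating room. These must be reconciled first.
- **That the primary comparison should be adjusted too.** Nothing in the documents shows how arrival skin temperature relates to the post-induction change in core temperature.

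**Conclusion.** The point holds for secondary endpoint 1, as a matter of precision and of an unsettled outcome choice. Adjusting for arrival skin temperature gives a variance between about 0.62 and 1.02 of the change-score variance over rho 0.2 to 0.6 and SD ratios of 1 to 2, with 20 per arm. The gain may be large or nil; the loss is at most about 3%. These figures rest on assumed correlations and SD ratios, a linear relation with a common slope, and a single covariate.

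The agreement between level and change analyses under adjustment needs no value of rho. It matters only if hypothesis 1a is read as a level.

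It would be wrong to conclude that the planned t-test is biased or invalid. For the PACU endpoint the benefit is conditional, and for the primary endpoint none is shown.

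**What to change.** In X.b, state that secondary endpoint 1 will be analysed by a linear model of departure skin temperature on arm, arrival skin temperature and the surgery-type stratum already used in the randomization (Study Procedures V). Report the treatment effect with its confidence interval. Say that this model also answers exploratory hypothesis 1a.

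In IX.b, state that the arrival reading is taken before warming starts. The protocol places both at arrival and does not give their order.

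Optionally, use the same covariate for PACU skin temperature, after endpoint 3 and IX.e have been reconciled.

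The cost is a sentence in each of X.b and IX.b, with no new measurement. Arrival temperature takes one degree of freedom (38 to 37) and at most about 3% in variance. The stratum takes one further degree of freedom (37 to 36), which the 37/36 factor does not include. The model also yields the residual SD and the arrival-to-departure relation, which a larger study would need.
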